3.0 PATIENT ELIGIBILITY

3.1 Inclusion Criteria

Participants must meet the following criteria on screening examination to be eligible to participate in the study:

Patient MRN:	Patient Initials (F, M, L):
--------------	-----------------------------

Informed Consent

1. All subjects must have the ability to understand and the willingness to sign a written informed consent.

Age Criteria, Performance Status, and Life Expectancy

2. Patients must be age \geq 18 years.

3. Patients must have a life expectancy of > 3 months.

4. Patients must exhibit an ECOG performance status of 0-2.

Nature of Illness and Treatment History

5. Patients must have a diagnosis of multiple myeloma.

6. Patients must have measurable disease, defined as one of the following within 21 days prior to registration:

- Serum M-protein ≥ 0.5 g/dL
- Urine M-protein ≥ 200 mg/24 hr
- Serum free light chain ≥ 10 mg/dL provided the FLC ratio is abnormal.
- 10% plasma cells in bone marrow

7. Patients must be relapsed or are refractory to at least 3 prior lines of therapy, including both a proteasome inhibitor and an IMiD, and for whom transplant is not recommended (induction therapy and stem cell transplant +/- maintenance will be considered as one regimen).

8. At least 2 weeks from prior therapy to time of start of treatment. Prior therapy includes steroids (except prednisone or equivalent – up to 10 mg per day is allowed).

Clinical laboratory parameters

9. Platelet count $\geq 50,000/\mu\text{L}$. Platelet transfusions are not allowed within 14 days of platelet assessment.

10. ANC $\geq 1000/\text{mm}^3$. Growth factor is not permitted within 14 days of neutrophil assessment.

11. AST and ALT $< 2.0 \times \text{ULN}$.

12. Total Bilirubin $< 1.5 \times \text{ULN}$.

13. Calculated creatinine clearance (CrCl) ≥ 30 mL/min per 24-hour urine collection or the Cockcroft-Gault formula.

$$\text{CrCl (mL/min)} = \frac{(140-\text{age}) \times \text{actual body weight (kg)}}{72 \times \text{serum creatinine (mg/dL)}} \quad (\times 0.85 \text{ for females})$$

Or

$$\text{CrCl (mL/min)} = \frac{(140-\text{age}) \times \text{actual body weight (kg)}}{0.8136 \times \text{serum creatinine (umol/L)}} \quad (\times 0.85 \text{ for females})$$

- 14. Negative serum or urine β -HCG test (female patient of childbearing potential* only), to be performed locally within the screening period.
- 15. Negative for tuberculosis antigen (e.g. T-Spot test).
- 16. Negative for hepatitis A, B, or C infection.
- 17. Adequate pulmonary function as defined by FVC and DLCO $\geq 50\%$ of predicted by pulmonary function testing.

Child Bearing Potential

- 18. Agreement by females of childbearing potential* and sexually active males to use an effective method of contraception (hormonal or barrier method of birth control or abstinence) prior to study entry and for three months following duration of study participation. The effects of study treatment on a developing fetus have the potential for teratogenic or abortifacient effects. Should a woman become pregnant or suspect that she is pregnant while participating on the trial, she should inform her treating physician immediately.

*A female of childbearing potential is defined as a sexually mature woman who: 1) has not undergone a hysterectomy or bilateral oophorectomy; or 2) has not been naturally postmenopausal for at least 24 consecutive months.

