2.0 BACKGROUND

2.1 Introduction/Rationale for Development

Multiple myeloma (MM) is a plasma cell malignancy characterized by periods of remissions and relapses. Worldwide, the incidence of MM is about 86,000 cases annually with about 63,000 deaths each year [4]. In the United States, over 30,000 patients are expected to be diagnosed with MM in 2016 and more than 12,000 patients will die from the disease [5, 6].

Treatments for MM include alkylating agents, immunomodulatory (IMiD) drugs, proteasome inhibitors, anthracyclines, and glucocorticoids. Therapeutic agents are used sequentially or in combination either as double, triple or quadruple chemotherapy combinations. While the prognosis for MM patients has improved [7, 8], MM remains an incurable disease with a median survival of approximately 3 to 4 years with standard therapy[9]. The 5-year survival rate for patients with MM is estimated at 46% (Cancer Statistics 2016), with only 17% of patients surviving for 10 years[10].

Relapsed and refractory multiple myeloma (RRMM) is defined as disease that is nonresponsive while on salvage therapy, or progressing within 60 days of cessation of the most recent prior therapy in patients who have achieved minimal response (MR) or better[11]. Primary refractory myeloma is defined as disease that is nonresponsive in patients who have never achieved a minimal response or better with any therapy[11]. The overall survival for patients who have received more than 3 prior regimens and whose disease has relapsed after treatment with bortezomib and lenalidomide is estimated to be between 6 and 10 months [12, 13]. Treatment decision making in the RRMM population is particularly challenging, given underlying comorbidities and the toxic nature of available agents. Moreover, duration of response to therapies is traditionally short due to multi-drug resistance as well as changes in disease biology (e.g., development of aggressive phenotype, higher proliferation rates, and lower apoptotic rates) [14]. Patients with RRMM are in dire need of new treatments with new mechanisms of action that could be used successfully long term.

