- Complete and email a Confirmation of Registration form within 24 hours to include the COH subject study number and dose level to the study team, which will include the Principal Investigator, treating physician, protocol nurse, CRC and COH IDS Pharmacy.
- Call the protocol nurse and/or CRC to verbally confirm registration.
- Enter the subject into Medidata RAVE®.
- A subject failing to meet all protocol requirements will not be registered.

Patients must begin protocol treatment within 1 week following registration date.

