10.0 STUDY CALENDAR

Table 10 describes required procedures. All procedures may increase in frequency if clinically indicated or oriented following toxicity. Adjustments to the treatment cycle due to a hold in study agent are detailed in [Section 5.2](#).

Table 10.0 Study Activity Calendar

	Screening ^a	Cycle 1, 2, 3		Cycle 4+ ^d	End of Treatment ^e				Active Follow-Up ^j	Long Term Follow-Up ^k
		Day 1 ^b	Day 14 ^c		Day 0 ^f	Days 1-11 ^g	Day 14 ^h	Day 30 ⁱ		
Informed Consent ^l	X ^u									
Inclusion/Exclusion Criteria ^m	X									
Registration ⁿ	X ⁿ									
Medical history ^o	X									
Physical exam	X	X		X					X	
Vital signs ^p	X	X		X					X	
Adverse events assessment ^q		X	X	X	X	X			X	
Concomitant meds review	X	X		X	X				X	
ECOG status ^r	X	X		X					X	
Pregnancy test ^s	X									
TB antigen test ^t	X									
Hepatitis A, B, C testing	X ^u									
Pulmonary function test	X ^u									
Extramedullary disease survey ^v	X ^u			X ^w	X ^w				X ^w	X ^w
Skeletal survey	X ^u									
Clinical bone marrow aspiration/biopsy with research use of leftover samples	X ^{u,y}	X ^{y,z,aa}		X ^{y,z}	X ^{y,z}				X ^{y,z}	X ^{y,z}
Research bone marrow aspiration		X ^{bb}								
CBC with differential ^{cc}	X	X	X	X					X	X
Chemistry panel ^{dd}	X	X	X	X					X	X
Myeloma labs ^{ee}	X	X ^{kk}		X	X				X	X
Response assessment ^{ff}		X ^{aa}		X	X				X	X
Research blood samples ^{gg}		X	X	X	X					
Teriflunomide clinical testing ^{hh}				X		X ⁱⁱ	X ⁱⁱ			
Leflunomide administration ^{jj}		Daily								
Cholestyramine ^g					X ^g					
Survival										X ^k

a. All screening procedures to be performed within 21 days of start of study agent except informed consent, acute hepatitis panel, skeletal survey, bone marrow biopsy, and pulmonary lung function test which may occur within 30 days of start of treatment (footnote u) and except for registration which must occur within 7 days from start of treatment (footnote n).

- b. Day 1 assessments to be performed within 5 days (120 hours) prior to Day 1 drug (except footnote u for C1 only). Day 1 safety assessments must be resulted and reviewed prior to administration of agent for the cycle that is initiating. Screening assessments, if performed within this aforementioned time frame, may serve as C1D1 assessments. Note: items with footnote "aa" are not performed for C1D1; the windows for screening assessments still apply.
- c. Day 14 evaluations have +/- 3 day window.

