- l. Informed consent process to be fully documented: e.g. prospective participant had sufficient time for deliberation, all questions were answered, treatment options provided by MD, full study reviewed including risks, and a copy of signed consent given to participant.
- m. Inclusion/exclusion criteria are detailed in [Section 3](#).
- n. See [Section 4.3](#) for slot reservation and registration process. Treatment must begin within 7 days of registration. Documentation providing Investigator's confirmation that all eligibility criteria are met must be available prior to registration.
- o. Medical history to include review treatment history for myeloma, medical history pertaining to eligibility, and demographic information.
- p. Vital signs: Weight, heart rate, blood pressure, respiration rate, temp. Height required only at baseline.
- q. Adverse event (AE) reporting begins for events that occur after start of study agent. AE recording and reporting will continue until the completion of the EOT Day 30 visit or until resolution or stabilization of any serious AE occurring before the completion the EOT Day 30 assessments, which every occurs later.
- r. See Appendix A for ECOG performance status criteria.
- s. Serum or urine pregnancy test for women of child bearing potential only.

- t. T-Spot or other TB antigen test.
- u. Consent, acute hepatitis panel, skeletal survey, bone marrow biopsy, bone marrow aspiration, and pulmonary lung function test to be completed within 30 days prior to registration.
- v. Extramedullary disease survey required at screening for all participants with known or suspected extra-medullary disease. May include CT scan of the abdomen/pelvis, CT or x-ray of the chest, ultrasound of the liver/spleen or abdomen. Technique used at screening/baseline (if applicable) should be used throughout the study and include tumor measurements.
- w. Extramedullary disease survey required after screening/baseline only in patients with extramedullary disease present at screening/baseline. To occur every 12 weeks or upon clinical suspicion of progressive disease.
- x. Skeletal survey (including skull, all long bones, pelvis and chest) with tumor measurements (if plasmacytomas are present). To be performed at baseline/screening and when clinically indicated.

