- y. Leftover bone marrow aspirate from screening/baseline, confirmation of complete response (CR/sCR, when applicable) and confirmation of progressive disease (PD, when applicable) ([Section 9.4](#)). Bone marrow aspirate will be collected into a 10mL or equivalent sodium heparin (green top) tube. Samples will be gently inverted approximately 8 times to mix the sample and then promptly taken at room temperature to [name] (Kaplan CRB, RM 3016) in [name] laboratory for processing (so that samples can be processed within an hour of collection). [name] ([contact]) as well as the supervisors [name] ([contact]) and [name] ([contact]) should be notified in advance of sampling (at least 1 day in advance) by email. Changes in laboratory contact information will not be considered protocol deviations.
- z. Perform bone marrow biopsy and/or aspirate once to confirm suspected CR, sCR, or PD.
- aa. Bone marrow and response assessments are not to be taken on Cycle 1 Day 1; screening labs will be used as baseline values.
- bb. Bone marrow aspiration for research on day 1 of cycle 2 ([Section 9.4](#)). **Note:** In the event that the research prep for the baseline bone marrow aspirate (footnote y) yields no useable product, this procedure will not be performed. In the event that this planned sample collection coincides with confirmation of suspected CR, sCR, or PD, then the clinical leftover samples (see footnotes y and z) will be used instead of a research-specific collection. See contact information for research sample transfer in footnote y.
- cc. CBC with differential: erythrocytes (RBC), hemoglobin, hematocrit, platelets, total WBC plus absolute differential counts (neutrophils, lymphocytes, monocytes, eosinophils, basophils).
- dd. Serum chemistry panel: Comprehensive metabolic panel (sodium, potassium, chloride, carbon dioxide, creatinine, urea nitrogen, calcium, glucose, albumin, total bilirubin, alkaline phosphatase, total protein, ALT/SGPT, AST/SGOT) LDH, magnesium, phosphorus, and uric acid.
- ee. Myeloma labs to include serum protein electrophoresis and immunofixation, quantitative immunoglobulins, serum free light chains and 24-hour urine studies (total protein, urine protein electrophoresis and immunofixation). Note: 24-hour urine studies to be performed at baseline for all participants, and after baseline to confirm complete response or in patients with urine-only measurable disease.

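### The response baseline may be drawn while prior anti-myeloma therapy is still being given, because the washout is counted from the first leflunomide dose and not from the baseline sample

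*Combined protocol and SAP*

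**What the plan says.** - **Washout.** Section 3.1, criterion 8: "At least 2 weeks from prior therapy to time of start of treatment". Steroids count as prior therapy, apart from a low daily prednisone-equivalent dose. Exclusion criterion 20 bars concurrent therapy during the study treatment period and refers back to criterion 8 for washout.
- **Lab window.** Section 10, footnote a: "All screening procedures to be performed within 21 days of start of study agent except informed consent" and a short list of other items. Marrow biopsy is on that list, with 30 days before start of treatment. Myeloma labs are not on it.
- **Response baseline.** Footnote aa rules out marrow and response assessment on Cycle 1 Day 1 and states that "screening labs will be used as baseline values".
- **Optional repeat.** Footnote kk lets the investigator repeat myeloma labs at Cycle 1 Day 1 and use them for response. Footnote b places Day 1 assessments in the 5 days before Day 1 drug.
- **Other reference dates.** Criterion 6: "Patients must have measurable disease, defined as one of the following within 21 days prior to registration". Footnote u lists marrow among tests ending with "pulmonary lung function test to be completed within 30 days prior to registration". Footnote n: "Treatment must begin within 7 days of registration".
- **General baseline line.** Section 6.2.1(c), on dose modification, takes baseline as the last value before treatment.

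**The concern.** Response in Table 11.2 is a percentage change from baseline, and the phase II objective is the activity of leflunomide given alone. That reading needs a baseline taken after other anti-myeloma treatment has ended. Here the washout is anchored to the first leflunomide dose, while the baseline sample is anchored to a longer window before that dose. Nothing ties the sample to the last prior dose.

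The protocol takes more care elsewhere: criteria 9 and 10 count the transfusion and growth-factor gaps back from the blood count itself.

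Two things are at stake. The first is the primary endpoint, the overall response rate, in an uncontrolled trial with a narrow decision margin (4 of 19, then 9 of 39). The second is the exploratory work. Baseline marrow supplies the ex vivo IC50 and the comparison with Cycle 2 Day 1 molecular profiles. Cells collected under the prior drug would mix the effect of its withdrawal with the effect of leflunomide.

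**Working it through.** **Timing.** Longest overlap = longest permitted look-back before first dose − minimum washout.

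- Myeloma labs (footnote a): 21 − 14 = 7 days of possible prior therapy after the baseline draw.
- Marrow (footnote a): 30 − 14 = 16 days.
- Cycle 1 Day 1 labs (footnotes b and kk): 5 − 14 = −9, so the draw falls at least 9 days after the last prior dose and there is no overlap.

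**Does another provision close the gap?**

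- Exclusion 20 covers only the study treatment period, which starts after the baseline draw.
- Section 6.2.1(c) is written for dose modification. It also does not help when the screening draw is the only draw.
- Footnote kk would help, but the repeat is discretionary and no rule says which value governs when both exist.
- Confirmation by two consecutive assessments (Table 11.2 notes) does not remove the problem, since both are compared with the same baseline.
- Marrow has no Cycle 1 Day 1 equivalent.

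**Inconsistent dates.** Criterion 6 counts 21 days from registration, and treatment may follow 7 days later: 21 + 7 = 28 days before start, against 21 in footnote a. Footnote u counts 30 days from registration: 30 + 7 = 37 days before start, against 30 in footnote a.

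**The plan's design figures.** Section 13.3: continue if X1 ≥ 4 of 19; worthy if the total is ≥ 9 of 39.

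- Early stopping = P(X1 ≤ 3 | n = 19, p). At p = 0.15 this is 0.684 (the plan states 0.68).
- P(worthy) = Σ over x = 4 to 19 of P(X1 = x) × P(X2 ≥ 9 − x | n = 20, p). At p = 0.15 this is 0.097 (limit 0.10); at p = 0.30 it is 0.803 (target 80%).

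The design is reproduced and is not in question.

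**Illustration.** The documents give no rate of misclassified responses, so the shifts below are assumptions put into the same formula.

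| Assumed shift | Apparent rate | P(worthy) | Early stopping |
|---|---|---|---|
| None, true rate 15% | 0.150 | 0.097 | 0.68 |
| One false response per 39 | 0.15 + 1/39 = 0.176 | 0.196 | 0.57 |
| Two false responses per 39 | 0.15 + 2/39 = 0.201 | 0.324 | 0.45 |
| None, true rate 30% | 0.300 | 0.803 | 0.13 |
| One masked response per 39 | 0.30 − 1/39 = 0.274 | 0.706 | 0.19 |

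**The case against.** The best defence is that the exposure is short and partly covered. Only 7 days of lab overlap are possible, footnote kk already offers a clean draw, and a partial response needs a fall of at least 50% seen twice. Patients entering after three or more lines are mostly not improving on their last one. Marrow enters the response rate only when serum, urine and free light chains are all unmeasurable and baseline plasma cells are at least 30%. The molecular and ex vivo aims are labelled exploratory. All of this limits the likely size. It does not close the gap, because whether a patient has a clean baseline remains an individual investigator's choice.

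Three stronger readings are tempting, and the documents do not support them.

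- **Longer overlaps.** Adding the 7 days from registration to criterion 6 and footnote u suggests 14 days for labs and 23 for marrow. A screening lab must also satisfy footnote a, so a draw 27 or 28 days before start would breach it, and footnote a likewise limits the marrow biopsy. The differing dates need reconciling; they do not grant the longest combination.
- **A faulty criterion 7.** Section 2.1 describes relapsed and refractory disease as including disease "progressing within 60 days of cessation of the most recent prior therapy", and criterion 7 has no such condition. But the trial also enrols relapsed patients, and Section 2.6 describes measurable disease after at least three regimens. Requiring progression on the latest regimen would narrow the population. That is a separate trade-off, not a correction.
- **Bias only in leflunomide's favour.** A sample drawn on therapy may understate the off-treatment disease level, and regrowth would then make a 50% fall harder to reach.

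**Conclusion.** The point holds in limited form. As written, the plan permits prior anti-myeloma therapy for up to 7 days after the response-baseline labs and up to 16 days after the baseline marrow, and no provision requires the baseline to follow the last prior dose. The timing result needs no assumption beyond reading footnote a as binding for screening labs.

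The effect on the response rate can go in either direction, and its size is unknown. It depends on how many patients are still being treated at screening and whether that treatment is still changing their disease. The rise from 0.097 to about 0.196 shows how sensitive the decision rule is to one misclassified response on average. A reader might infer that the trial's real type I error is doubled; the documents give no basis for that.

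**What to change.** Amend footnotes aa and kk so that the response baseline is a myeloma-lab draw taken after the last dose of prior anti-myeloma therapy. The simplest way is to make the Cycle 1 Day 1 draw, within 5 days before Day 1 drug, required and governing. Footnote b already lets a screening draw inside those 5 days serve, so such patients need no repeat. Reconcile the reference dates of criterion 6 with footnote a, and of footnote a with footnote u.

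In the ex vivo analyses and the baseline versus Cycle 2 Day 1 molecular comparison, flag or exclude baseline marrow taken before the last prior dose, at least as a sensitivity analysis. Apply the same flag to any patient whose response is judged on marrow.

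The cost is protocol wording, one repeat blood draw for some patients (with a repeat 24-hour urine collection where response is followed in urine), and a few exploratory marrow samples lost. The design, sample size and visit schedule do not change. The amendment removes overlap with prior dosing. It does not remove all late effect of a prior drug, and the report should say so.

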3.2 Exclusion Criteria

Prospective participants who meet any of the following criteria will not be eligible for admission into the study:

Previous therapies

- 19. Prior treatment with leflunomide.

Concomitant medications

- 20. Current or planned use of other investigational agents, or concurrent biological, chemotherapy, or radiation therapy during the study treatment period. (See inclusion criterion #8 for washout times).
- 21. Current or planned growth factor or transfusion support until after initiation of treatment. If growth factor or transfusion support is provided between screening and start of treatment, the participant will no longer be eligible.

Other illnesses or conditions

- 22. Prior diagnosis of rheumatoid arthritis.
- 23. Prior Allogeneic transplant.
- 24. Acute active infection requiring systemic therapy within 2 weeks prior to enrollment.

- 25. Pre-existing liver disease.
- 26. Known HIV infection.
- 27. History of allergic reactions attributed to compounds of similar chemical or biologic composition to leflunomide or cholestyramine.
- 28. Non-hematologic malignancy within the past 3 years aside from the following exceptions:
 - adequately treated basal cell or squamous cell skin cancer
 - carcinoma in situ of the cervix
 - prostate cancer < Gleason Grade 6 with a stable PSA
 - successfully treated in situ carcinoma of the breast
- 29. Clinically significant medical disease or condition that, in the investigator's opinion, may interfere with protocol adherence or the patient's ability to give informed consent.
- 30. Pregnant women and women who are lactating. Leflunomide has potential for teratogenic or abortifacient effects. Because there is a potential risk for adverse events in nursing infants secondary to treatment of the mother with these agents, breastfeeding should be discontinued if the mother is enrolled on this study.
- 31. Any other condition that would, in the Investigator's judgment, contraindicate the patient's participation in the clinical study due to safety concerns or compliance with clinical study procedures, e.g., infection/inflammation, intestinal obstruction, unable to swallow medication, social/ psychological issues, etc.

Noncompliance

- 32. Prospective participants who, in the opinion of the investigator, may not be able to comply with all study procedures (including compliance issues related to feasibility/logistics).

